## 5 Study design

### 5.1 Type of study

This study is a post-authorisation commitment to the European Medicines Agency – a Post Authorisation Safety Study (PASS) - to monitor the long-term safety of Levemir® in pregnant women to cover the gestation and lactation. This international, prospective, non-interventional, multi-centre cohort study will monitor and assess the safety of Levemir® use during pregnancy as well as monitoring the health status of the infants at 1 month and at 1 year of age. The same parameters will also be monitored and assessed for other injectable antidiabetic treatment regimens.

The study is non-interventional as the assignment of the patient to a particular therapeutic strategy is not decided in advance by a trial protocol but falls within current practice and the prescription of the medicine is clearly separated from the decision to include the patient in the study.

Enrolment of women on injectable antidiabetic treatment regimens will most likely also include women treated with injectable antidiabetic drugs apart from insulins. Treatment with such injectable antidiabetic drugs for example GLP-1 agonists during pregnancy is off-label use. Due to the non-interventional study design of the Diabetes Pregnancy Registry women treated with injectable antidiabetic drugs other than insulins will be included either if they are treated with other injectable antidiabetic drugs solely or treated with a combination of insulin and other injectable antidiabetic drugs. The information on all insulins and other injectable antidiabetic treatment regimens is collected for the completeness of the non-interventional real-world data collection in order to obtain a comprehensive overview of the treatment patterns used in pregnant women with DM.

Change in dosage, dose interval and add-on or removal of bolus insulin, oral antidiabetic drugs and/or GLP-1 agonists is expected and will not exclude pregnant women to participate in the registry and in the primary and secondary endpoint analysis. A change in type or brand of basal insulin after baseline visit will lead to exclusion from the primary and secondary endpoint analysis, but not from the registry itself.

The study period includes the gestation periods of the pregnant women and the follow-up of the infants at 1 month and at 1 year of age.

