### **5.4 Limitation of study design and data sources**

Due to the exploratory nature of the study, the results will contribute to the current knowledge regarding treatment of pregnant women with both insulins and other injectable antidiabetic treatment regimens. A substantial high number of patients in the registry will enable confirmation of existing evidence from clinical studies and a generation of new hypotheses with respect to the long-term safety of Levemir® and other injectable antidiabetic treatment regimens in pregnant women with DM and their infants.

A heterogeneous patient population and different local requirements with regard to the routine patient management may limit the explanatory power of the study results if not well-adjusted in the analysis part. Heterogeneity will, however, be minimal in the present registry as the study sites have many similarities with regard to standard routine procedures in the treatment of pregnant women with DM. Confounding factors and other relevant background covariates will be collected at the baseline visit in order to adjust for relevant factors in the statistical analysis.

Protocol  
Study ID: NN304-4016  
UTN No: U1111-1132-9442  
EU PAS No.: ENCEPP/SDPP/4137

~~CONFIDENTIAL~~

Date: 08 September 2017  
Version: 6.0  
Status: Final  
Page: 21 of 60

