## 8 Methods and assessments

The Diabetes Pregnancy Registry will include maternal and paediatric assessments as per standard practise. There are differences in the endpoints covering the gestation period, the delivery, the pregnancy outcomes, the postpartum visit and the follow-up in the infants. The variables on the study forms will depend on these different endpoints.

All parameters which will be collected in this registry are defined in accordance with normal clinical practice. Relevant registry forms for the baseline visit including potential confounders, standard routine visits, delivery visit, the postpartum visit and the follow-up of the infants are developed together with some of the study sites participating in the registry.

Signed informed consent must be obtained prior to any data entry into the registry.

After the Informed Consent Form has been signed, patients will be allocated an ID number, which will remain unchanged throughout the study. The physician will assign each enrolled patient with a unique 6 digit patient number. The patient number is composed of 3 digits unique for each study site followed by 3 consecutive digits for each enrolled patient on the study site. If an eligible woman is included in the Diabetes Pregnancy Registry more than once, she will be allocated a new patient ID number for each pregnancy that may occur during the recruitment period. The infant(s) of the patient will be allocated the same ID number as its mother followed by a "Xn" at the end of the 6 digit patient number (n=1, 2, 3 and so forth for each child).

Patients enrolled in the study will be provided with contact address and telephone number of the physician site and/or staff.

In case a patient is withdrawn from the study the physician will ensure that the primary reason for discontinuation will be specified in the eCRF.

This section describes the general study procedures applicable for all patients. Visit and contact specific procedures are described in sub-sections below.

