### **8.3 Other assessments**

#### **8.3.1 Demographics**

The following maternal information will be recorded at baseline visit:

- Date of birth
- Race
- Socioeconomic status (education, occupation)
- Recreational drug use
  - Tobacco (y/n, how much/day)
  - Alcohol (y/n, how much/day)
  - Other (y/n, how much/day)

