#### 14.4 Statistical methods

All endpoints will be analysed on the analysis set.

Continuous variables (maternal HbA1c at start of pregnancy, at the end of each trimester, and height and weight of the infant at 1 year) will be summarised with descriptive statistics (number of observations with available values, number of observations with missing values, mean, 95% confidence interval of the mean, standard deviation, minimum, median, maximum), and categorical variables and Apgar score will be displayed in frequency tables (N, %). The mean of the Apgar score will also be computed.

The primary endpoint, proportion of pregnancies resulting in the combined pregnancy outcome will be computed for the Levemir® group, and for the other basal insulin group, the difference between these proportions will be computed along with the 95% confidence interval and the p-value using Fisher's exact test. This simple analysis might be biased if type of basal insulin is confounded with other risk factors for a negative birth outcome, so to take this into account the primary endpoint will also be analysed using logistic regression, see the description below.

This analysis will be performed for all other endpoints which are proportions, both maternal endpoints, pregnancy outcome endpoints, and infants' endpoints at 1 year of age.

In addition, the primary endpoint will be analysed using logistic regression. Both crude and adjusted models will be performed. The model will include treatment group (Levemir®/other basal insulins group), and adjust for potential confounders such as study site, type of DM, race, hypertension, major hypoglycaemic events during pregnancy, folic acid intake, and use of GLP-1 agonists during pregnancy. Furthermore, HbA1c at start of pregnancy, end of first trimester, and end of second trimester, age and BMI of the woman at baseline, duration of DM, blood pressure and previous foetal pregnancy complications will be adjusted for as appropriate. Adjustments will be performed in a stepwise manner, and further specified in the Statistical Analysis Plan. Similar analyses will be performed for all other endpoints which are proportions for maternal endpoints, or proportions for pregnancy outcome endpoints.

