For the infants endpoints at 1 year of age the proportions will also be analysed using logistic regression, the model will include treatment group (Levemir®/other basal insulins group), study site, race, hypertension, major hypoglycaemic events during pregnancy, folic acid intake, and possible use of GLP-1 agonists during pregnancy as factors. Furthermore, HbA1c at start of pregnancy, end of first trimester, and end of second trimester, age and BMI of the woman at baseline, duration of DM, blood pressure and previous foetal pregnancy complications will be included as covariates. The analyses regarding height and weight will also be adjusted for exclusive and/or partial lactation period.

The means of the continuous endpoints (maternal HbA1c at the end of each trimester and, height and weight of the infant at 1 year), will be compared between the Levemir® group and the other basal insulins group using an analysis of covariance (ANCOVA) model.

The incidence of major hypoglycaemia during pregnancy will be computed for both treatment groups.

Additional exploratory hypothesis-generating analyses may also be performed as deemed relevant.

Differences in gestational age at study entry and exact follow-up time will be taken into account in the statistical analysis where relevant.

All statistical analyses will be performed using appropriate statistical software. All statistical tests will be performed as two-sided tests with a significance level of 0.05.

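### The closed adjustment list for the 1-year infant endpoints omits maternal smoking and socioeconomic status, although both are recorded at baseline, leaving infant height and weight open to avoidable confounding

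*Protocol*

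**What the plan says.** Treatment follows routine care: section 5.1 states that "assignment of the patient to a particular therapeutic strategy is not decided in advance by a trial protocol but falls within current practice". Section 5.4 gives the intended remedy: "Confounding factors and other relevant background covariates will be collected at the baseline visit in order to adjust for relevant factors in the statistical analysis". Section 8 describes the baseline forms in the same spirit ("Relevant registry forms for the baseline visit including potential confounders").

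Among the baseline items in section 8.3.1 are "Tobacco (y/n, how much/day") and "Socioeconomic status (education, occupation").

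Section 14.4 then gives two adjustment lists.

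- **Primary, maternal and pregnancy-outcome proportions.** The variables are offered as examples of potential confounders. The last group, ending "duration of DM, blood pressure and previous foetal pregnancy complications will be adjusted for as appropriate", is conditional, and the stepwise adjustment is left to the SAP for detail.
- **1-year infant endpoints.** The logistic model for the proportions has named factors and then covariates: "age and BMI of the woman at baseline, duration of DM, blood pressure and previous foetal pregnancy complications will be included as covariates". Nothing marks these as examples, and the covariates are not deferred to the SAP. A further sentence says that height and weight are additionally adjusted for lactation period. The later ANCOVA sentence names no covariates of its own.

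Neither list names tobacco, education or occupation. The Summary lists infant height and weight at 1 year among the key secondary endpoints.

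**The concern.** In a non-randomised comparison, covariate adjustment is the main protection against differences between the women who use each insulin. Section 14.4 accepts this for the primary endpoint, where it warns that the simple comparison might be biased.

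Maternal smoking and social position are plausible determinants of infant growth, and either could differ between women prescribed different basal insulins. Both are measured before the outcome and are on the baseline form, so adjusting for them carries no risk of removing part of a treatment effect. That cannot be said of some terms the infant list does include, such as major hypoglycaemia during pregnancy and HbA1c later in pregnancy.

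A statistician who follows the infant list as written would fit the height and weight models without these two variables. Adding them after the results are seen would invite the charge of choosing covariates post hoc, in a safety study done as a regulatory commitment.

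**Working it through.** The protocol states no figure on this point, so the main check sets the baseline items against the lists.

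**1. What the infant list contains (section 14.4), apart from treatment group**

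| Group | Variables | Count |
|---|---|---|
| Factors | study site, race, hypertension, major hypoglycaemia in pregnancy, folic acid, GLP-1 agonist use | 6 |
| HbA1c | start of pregnancy, end of first trimester, end of second trimester | 3 |
| Other covariates | age, BMI, diabetes duration, blood pressure, previous foetal pregnancy complications | 5 |
| Height and weight only | lactation period | 1 |

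That is 14 variables, or 15 for height and weight. None is tobacco use, education or occupation.

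**2. Is the list open or closed?** The list for the primary and related endpoints is illustrative, conditional and deferred to the SAP. The infant list has none of these features. The height and weight sentence says lactation is adjusted for as well, which reads most naturally as the same list plus lactation.

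**3. Does study site stand in for the missing variables?** Site absorbs differences between clinics, including much of any national or reimbursement effect. It cannot remove differences between women attending the same clinic.

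**4. Form of the bias.** The inputs below are assumptions, not protocol figures. Treat smoking as yes/no, with prevalence p1 and p0 in the two groups, no true insulin effect, and no correlation with variables already in the model.

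- *Height or weight.* The spurious mean difference is (p1 − p0) × δ, where δ is the mean difference between infants of smokers and of non-smokers. With 10% in one group and 15% to 30% in the other, its size runs from 0.05 × δ to 0.20 × δ. The protocol gives no δ, so this cannot be turned into centimetres or kilograms. If p1 = p0, it is zero.
- *Infant proportions.* The spurious risk ratio is (1 + p1(RR − 1)) / (1 + p0(RR − 1)), where RR is the effect of smoking on the outcome. At 10% v 15% and RR 1.3: 1.03 / 1.045 = 0.986. At 10% v 30% and RR 2.0: 1.10 / 1.30 = 0.846.

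These assumptions span negligible to material. They show how the bias would behave, not how large it is in this registry.

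**5. Room for extra terms.** The plan is for 1,222 pregnancies in the primary analysis (section 6.1). Fewer infants will have 1-year data, but height and weight are continuous, so one or two more variables should be affordable. The infant proportions differ. At the 4.5% major-malformation rate in section 14.2, 0.045 × 1,222 ≈ 55 pregnancies would involve one. If change in malformation is assessed among those infants, a model with 14 named variables is already hard to estimate.

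**The case against.** Several objections have force.

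- **A reader might infer that the primary, maternal and pregnancy-outcome models also leave smoking and social position out.** The document does not support that. Their list is open and deferred to the SAP, which is not at hand, so nothing excludes the two variables there.
- **A reader might infer that the insulin comparison is shown to be biased.** It is not. The protocol gives no smoking or socioeconomic imbalance and no effect size. Race, age, BMI, folic acid, HbA1c and previous complications may also capture part of social position, which would shrink any residual bias.
- **A reader might take section 5.4 as a promise to adjust for these two variables.** It speaks of relevant factors in general. Alcohol, asthma, epilepsy and thyroid disorder are also recorded and not listed.
- **The closed wording strictly governs the infant proportions.** The ANCOVA sentence lists no covariates, so the set for height and weight is inferred from the sentence on lactation. This is fair, but either reading calls for the same correction: state the set and include the two variables.
- **The study is described as exploratory, and further exploratory analyses are allowed.** Those would not alter the planned model.

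What remains is a named list that, for infant growth, passes over two recorded baseline variables.

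**Conclusion.** The point holds for the 1-year infant endpoints, and chiefly for height and weight. Followed as written, section 14.4 omits baseline tobacco use and socioeconomic status from a non-randomised comparison, although the data are collected and section 5.4 says baseline confounders are collected for adjustment.

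The conclusion rests on two assumptions: that smoking or social position affects infant growth, and that either may differ by insulin group after the listed adjustments. The size of the bias cannot be derived from the documents and is nil under balance. The change is worth making because it costs almost nothing, not because harm has been demonstrated. It does not call the primary analysis into question.

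**What to change.** In the infant paragraph of section 14.4:

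1. State the covariates of the ANCOVA models for infant height and weight explicitly. Include baseline tobacco use (none, or categories of amount per day) and education, or another recorded socioeconomic measure.
2. Open the list for the infant proportions in the same way as the list for the primary endpoint, and add the two variables there only where event numbers allow.

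Optionally, name both variables among the examples for the primary, maternal and pregnancy-outcome models, or in the SAP.

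No new data are needed. The cost is one or two more terms per model, and some loss of records where tobacco or education is missing. Section 8.1 expects missing data, so the handling of these gaps should be stated with the change.

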### **KEY SECONDARY OBJECTIVES:**

#### *Maternal*

Comparison of the following adverse events and abnormal metabolic control in pregnant women treated with Levemir® to pregnant women treated with other basal insulin regimens:

- Incidence of major hypoglycaemic events during the pregnancy period
- Development of pre-eclampsia during pregnancy

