### **KEY SECONDARY ENDPOINTS:**

#### **Maternal endpoints**

- Incidence of major hypoglycaemia during pregnancy
- Proportion of pregnancies complicated by pre-eclampsia during pregnancy

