#### 4.1.2 Secondary objective

##### *Maternal*

Comparison of the following adverse events and abnormal metabolic control in pregnant women treated with Levemir® to pregnant women treated with other basal insulin regimens:

- Incidence of major hypoglycaemic events during the pregnancy period
- Development of pre-eclampsia during pregnancy
- Metabolic control measured as HbA1c during pregnancy

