### **4.2.2 Secondary endpoints**

#### **4.2.2.1 Maternal endpoints**

- Incidence of major hypoglycaemia during pregnancy
- Proportion of pregnancies where the woman experiences at least one major hypoglycaemic event during pregnancy
- Proportion of pregnancies complicated by pre-eclampsia during pregnancy
- HbA1c level assessed as close as possible to conception, end of first trimester, end of second trimester, and at delivery.

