### **8.3.8 Major hypoglycaemic events**

Major hypoglycaemia is defined as a hypoglycaemic episode where the patient is not able to treat him/herself and where oral carbohydrates, glucagon or intravenous glucose has to be administered to the patient by another person because of severe central nervous system dysfunction.

The woman will be asked at any visit/contact whether she has experienced any major hypoglycaemic events since last study visit/contact (y/n and if yes how many). These events should be reported according to section [9](#).

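### Section 14.4 only tabulates the incidence of major hypoglycaemia by group, although the maternal objective is to compare it between groups

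*Protocol*

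**What the plan says.** The maternal objective, in both the Summary and section 4.1.2, opens with "Comparison of the following adverse events and abnormal metabolic control in pregnant women treated with" Levemir against women on other basal insulins. Its first item is "Incidence of major hypoglycaemic events during the pregnancy period".

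The Summary lists two key secondary maternal endpoints. One is "Incidence of major hypoglycaemia during pregnancy"; the other is pre-eclampsia. Section 4.2.2.1 repeats the incidence endpoint and lists a second hypoglycaemia endpoint beside it: "Proportion of pregnancies where the woman experiences at least one major hypoglycaemic event during pregnancy".

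Section 8.3.8 has the woman asked about major events since the last contact, recorded as "y/n and if yes how many". Event counts are therefore collected.

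For incidence, the analysis in section 14.4 is one sentence: "The incidence of major hypoglycaemia during pregnancy will be computed for both treatment groups".

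**The concern.** The objective asks how the two groups differ in the frequency of major hypoglycaemic events. The stated analysis yields one figure per group and stops there. A reader of the report would have no estimate of the difference, no measure of its precision, and no protection against confounding.

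The last of these matters because the study is a non-randomised cohort. Section 14.4 itself concedes that an unadjusted comparison of the primary endpoint could be biased if the choice of basal insulin goes with other risk factors, and it adds logistic regression for that reason. The same reasoning applies to hypoglycaemia, yet the incidence endpoint gets neither the unadjusted comparison nor the adjusted one.

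**Working it through.** The protocol states no figure for this endpoint, so there is nothing to recompute. The check maps each hypoglycaemia objective and endpoint to its stated analysis.

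1. **Is the objective comparative?** Yes. Both the Summary and section 4.1.2 frame the maternal items as a comparison of Levemir with other basal insulin regimens, and incidence of major hypoglycaemic events is the first item.

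2. **What does section 14.4 provide for each type of endpoint?**

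| Endpoint type | Stated analysis | Between-group estimate or test? | Confounder adjustment? |
|---|---|---|---|
| Proportions, including maternal ones | Difference, 95% CI, Fisher's exact test; crude and adjusted logistic regression | Yes | Yes |
| Continuous (HbA1c, infant height and weight) | ANCOVA comparison of means | Yes | Through the ANCOVA model |
| Incidence of major hypoglycaemia | A figure for each group | None stated | None stated |

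For the first row the text is explicit: "This analysis will be performed for all other endpoints which are proportions, both maternal endpoints", and for the regression, "Similar analyses will be performed for all other endpoints which are proportions for maternal endpoints". Where section 14.4 intends a comparison it says so. Incidence is the one listed type for which it does not.

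3. **Could incidence be read as a proportion and so fall under the first row?** Section 4.2.2.1 lists the at-least-one-event proportion as a separate endpoint. If incidence meant the same thing, one of the two entries would be redundant. Section 8.3.8 also collects the number of events, which a yes/no proportion does not need. The natural reading is that incidence is an event count or rate, and the methods for proportions do not cover it.

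4. **Is the gap filled elsewhere in section 14.4?** Two other sentences come close. One says that differences in gestational age at entry and in follow-up time will be allowed for where relevant. It is general, is not linked to hypoglycaemia, and describes no contrast. The other permits additional exploratory analyses. These are optional and cannot be relied on to deliver a listed secondary objective.

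5. **What part of the objective is answered?** The at-least-one-event proportion is a maternal proportion, so it receives the full set in the first row. Whether a woman had any major event is therefore compared, crude and adjusted. How many events she had is not: a woman with one event and a woman with several count the same.

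**The case against.** The strongest reply has four parts.

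- **Hypoglycaemia is compared.** The at-least-one-event proportion gets a difference, an interval, a test and an adjusted model. This stands. A reader might infer from the incidence sentence that the hypoglycaemia objective goes unanswered altogether; the document does not support that.

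- **Observation time is addressed.** A reader might infer that it is ignored, since entry may be at any time up to 16 weeks and women are therefore followed for different periods. The general sentence on entry and follow-up time prevents that conclusion. Unequal entry would also bias a group comparison only if entry timing differed between the groups, and nothing in the protocol shows that it does. What remains is that the sentence is not tied to this endpoint and provides no comparison.

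- **The details belong in the statistical analysis plan.** The choice of count model, offset and treatment of overdispersion can properly be left there, and their absence from the protocol is no fault. A plan not shown here may already contain a rate model. But section 14.4 is not silent on incidence: it states an analysis, and that analysis falls short of the objective. Its explicit deferral to the statistical analysis plan concerns the stepwise adjustments. Nor does the protocol plan a Poisson or other interval for incidence that could be criticised as too narrow.

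- **The key label appears only in the Summary.** Sections 4.1.2 and 4.2.2.1 set no key tier, and no testing order depends on it. This stands and lowers the stakes. The mismatch does not depend on the label, because section 4.1.2 sets the same comparison without it.

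**Conclusion.** The point holds as a mismatch between objective and method. The protocol sets out to compare the incidence of major hypoglycaemic events and lists incidence as a key secondary endpoint in its Summary, but section 14.4 provides only one figure per group, with no contrast, interval or adjustment. The objective is partly answered through the at-least-one-event proportion, which leaves repeat events out.

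The size cannot be given as a number. Section 3.1 cites reports that up to 71% of pregnant women with diabetes have major episodes, so repeat events may well be common, but the protocol gives no events per woman or event rate for either group. Any figure for lost information or bias would rest on assumed entry times or assumed overdispersion and would not measure this defect.

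The conclusion rests on one reading: that incidence means an event count or rate. The separate listing of the proportion endpoint and the collection of event counts support it. The conclusion does not claim that no comparison will ever be made. It should be corrected, but it does not touch the primary endpoint.

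**What to change.** Replace the incidence sentence in section 14.4 with one of the following.

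- **Preferred.** The number of major hypoglycaemic events from the baseline visit to delivery or pregnancy termination is compared between the Levemir and other basal insulin groups as a rate ratio with 95% CI. Use a count model that allows for overdispersion, such as negative binomial regression, with log time at risk as offset and adjustment for baseline confounders. The section 14.4 covariate for major hypoglycaemic events during pregnancy must be left out, since here it is the outcome.

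- **Alternative.** Declare incidence descriptive, name the at-least-one-event proportion as the key comparative hypoglycaemia endpoint, and align the Summary and section 4.1.2. The same covariate must then be left out of that endpoint's logistic model.

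The preferred option costs one sentence and one extra model. It needs no new data: event counts are collected under section 8.3.8, gestational dating under 8.3.7, and the date or gestational week of the outcome under 8.3.11 and 8.3.12. The alternative costs wording only, but gives up any comparison of repeat events. If the statistical analysis plan already contains a rate comparison, bringing the protocol sentence into line with it is enough.
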